#### Quantitative Eyebrow Lift

Treatment-related lift in eyebrow position on frontal view will be measured by calculating the differences in eyebrow height using baseline and Day 90 and Day 180 images.

Quantitative results will be calculated using five evenly spaced points on the brow. Height will be calculated at each of the five points and subsequently averaged to generate the average eyebrow height (AEH). Eyebrow lift will be indicated by the calculated change in AEH between baseline and Day 90 and Day 180 height of the brow. For the calculation of change in AEH, only datapoints with non-missing values for both visits (baseline and either Day 90 or Day 180) will be used.

[figure not shown]
To assess eyebrow lift from baseline to Day 90 and Day 180, the proportion of responders, defined as subjects achieving  $\geq 0.5$  mm eyebrow lift at Day 90 and Day 180 compared to baseline, will be described by frequency statistics for observed cases in the ITT. Success for the quantitative eyebrow lift will be established if the lower bound of the one-sided 95% Wilson CI for proportion of responders is  $> 50\%$ .

Time course of absolute values and changes from baseline in mm will be described by metric statistics. Additionally, the change in height from baseline at Day 90 and Day 180 will be calculated for each brow point, and maximum eyebrow height change (MEH) will be presented as maximum over all brow points over both sides.

These analyses will be provided by facial side (left/right) and overall. For the overall analysis, a subject will be responder if  $\geq 0.5$  mm eyebrow lift for both sides is achieved, while metric statistics will be based on the average of the right and left sides on frontal view.

CCI

CCI

CCI

## 6.2 Safety Endpoints

All safety analyses will be summarized for observed values in the SP.

### 6.2.1 Primary Safety Endpoint

Not applicable.

### 6.2.2 Secondary Safety Endpoints

All AEs will be coded according to the Medical Dictionary for Regulatory Activities (MedDRA) version in effect at the time the database is closed.

Only treatment-emergent AEs (TEAEs) will be analyzed, which are defined as AEs with onset or worsening at or after the first administration of study treatment. In this regard, an AE, with onset prior to treatment, that worsens at or after first administration of study treatment must be documented as a new TEAE with onset at the time of worsening.

An overall summary of AEs will be provided for the following:

- Any AEs;
- Any non-TEAEs;
- Any TEAEs;
- Any treatment-related TEAEs;
- Any serious TEAEs;
- Any serious treatment-related TEAEs;
- Any TEAEs leading to discontinuation;
- Any treatment-related TEAEs leading to discontinuation;
- Any fatal TEAEs, and
- Any treatment-related fatal TEAEs.

Incidence will be provided for the following classes of AEs:

- TEAEs, subjects with TEAEs and number of TEAEs by MedDRA system organ class (SOC) and preferred term (PT);
- TEAEs, subjects with TEAEs by PT;
- Non-TEAEs, subjects with Non-TEAEs and number of Non-TEAEs by SOC and PT;
- Non-serious TEAEs, subjects with TEAEs and number of TEAEs by SOC and PT;
- TEAEs by maximum intensity (mild, moderate, severe), subjects with TEAEs by PT;
- TEAEs by worst causal relationship (related, not related), subjects with TEAEs by PT;
- TEAEs by worst outcome, subjects with TEAEs by PT;
- TEAEs by affected treatment area, subjects with TEAEs by PT;
- TEAEs by maximum duration (1-3 days, 4-7 days, 8-14 days,  $\geq 15$  days), subjects with TEAEs by PT;

- TEAEs by maximum duration and maximum intensity, subjects with TEAEs by PT;
- Related TEAEs, subjects with TEAEs and number of TEAEs by SOC and PT ;
- Related TEAEs, subjects with TEAEs by PT;
- Non-serious related TEAEs, subjects with TEAEs and number of TEAEs by SOC and PT;
- Related TEAEs by maximum intensity, subjects with TEAEs by PT;
- Related TEAEs by worst causal relationship, subjects with TEAEs by PT;
- Related TEAEs by worst outcome, subjects with TEAEs by PT;
- Related TEAEs by affected treatment area, subjects with TEAEs by PT;
- Related TEAEs by maximum duration (1-3 days, 4-7 days, 8-14 days,  $\geq 15$  days), subjects with TEAEs by PT;
- Related TEAEs by maximum duration and maximum intensity, subjects with TEAEs by PT;
- Serious TEAEs, subjects by SOC and PT;
- Related serious TEAEs, subjects by SOC and PT;
- Serious TEAEs, listing of subjects (in case of more than 15 serious TEAEs respective table by PT and SOC will be provided); and
- Related serious TEAEs, listing of subjects (in case of more than 15 related serious TEAEs respective table by PT and SOC will be provided).

All tables will be sorted by descending frequencies in Preferred Terms (within SOCs).

The duration of AEs will be calculated by the difference of start and stop day plus 1.

If a subject has more than one outcome within a PT only the worst outcome in the respective time period will be used in the frequency tables. Also on subject level, only the worst outcome category per subject in the respective time period will be counted in the frequency table. The worst outcome is defined in the following order (from best to worst):

- recovered/resolved
- recovered/resolved with sequelae
- recovering/resolving
- not recovered/not resolved
- unknown
- fatal

[figure not shown]
Moreover, incidences of TEAEs, by PT and SOC, will be provided for the following subgroups:

- Race
- Fitzpatrick Skin Types (I, II, III versus IV, V, VI).

Listings for all AEs, as well as subsets including AEs leading to discontinuation, related SAEs, and deaths, will be provided. AEs with delayed onset will be flagged. A delayed onset AE is defined as an AE with an onset more than 28 days after treatment.

Treatments discontinued due to pain and device deficiencies will also be listed.

CCI

## **Disposition of subjects**

The absolute and relative frequencies for subjects' main reason for premature study discontinuation will be tabulated, based on all treated subjects. Furthermore, the number of subjects screened, the number of subjects treated, and the number of subjects in respective analysis sets will be tabulated.

Visit attendance will be presented in a frequency table for all treated subjects. For 'Subjects expected at visit', the following visits, at a minimum, are defined as expected for all treated subjects: Screening and Day 1 (Baseline). For subjects without reconsent in Stage 1, all following telephone contacts and visits are expected until Day 90 or premature study discontinuation, whatever occurs first. For subjects in Stage 1 with reconsent and all subjects in Stage 2, all following telephone contacts and visits are expected until regular study completion at Day 180 or premature study discontinuation, whatever occurs first. For subjects who discontinue the study, the end of study visit (Day 90 for subjects without reconsent or Day 180 for subjects with reconsent) is expected. Visits after premature discontinuation are generally not expected.

Percentages of 'Subjects expected at visit' will be calculated relative to the total number of treated subjects for Screening visit until Day 90 visit and relative to the number of subjects with reconsent from TC (Day 121) until Day 180 visit.

Percentages relating to 'Visit performed' and 'Visit not performed' will be calculated relative to the number of subjects expected at the respective visit. For study discontinuations, only absolute numbers will be displayed.

### **Protocol deviations**

The absolute and relative frequencies of subjects with major protocol deviations and other reasons for exclusion from analysis sets will be tabulated, based on all treated subjects.

### **Demographic data and baseline characteristics**

Demographic data will be summarized for the SP, the ITT, and the PP. Fitzpatrick skin type will be presented by original value as well as by categories type I-III and type IV-VI. Age will additionally be presented by categories <35 years, 35-40 years, 41-50 years, 51-60 years, 61-65 years and >65 years.

### **Previous and concomitant medications and non-drug treatments**

Separation of previous from concomitant medications will be done according to the start and stop date of the medication in comparison to the date of treatment. Each medication will be allocated unambiguously either to previous medication or to concomitant medication.

- Previous medication: If stop date is before start of treatment.
- Concomitant medication: If the start date is at or after start of treatment or if the stop date is at or after start of treatment or ongoing is ticked.

Previous and concomitant medications will be coded by use of the World Health Organization Drug Dictionary (WHO-DD) whereby the version in effect at the time the database is closed will be used.

Frequencies of previous and concomitant medications will be given on the basis of various Anatomical Therapeutic Chemical classification system of the World Health Organization (ATC) code levels for the SP. Indications for concomitant medications will not be coded and will only be listed.

Non-drug treatments will be coded using MedDRA version which is in effect at the time the database is closed. Non-drug treatments will be reported by SOC and PT levels for the SP.

## **Medical history and concomitant diseases**

Separation of medical history from concomitant diseases will be done according to the stop date of the finding in comparison to the day of treatment. Each finding will be allocated unambiguously either to medical history or to concomitant diseases.

- Medical history: If stop date is before start of treatment.
- Concomitant disease: If the stop date is at or after start of treatment or ongoing is ticked (even if it refers to a cut-off point before start of treatment).

Rules for separation of medical history and concomitant diseases for missing or incomplete dates are given in the Appendix.

Medical history and concomitant diseases will be coded using the MedDRA dictionary and reported by SOC and PT levels for the SP.

## **Pain pre-treatment medication**

Frequency tables of pre-treatment pain medication (initial, additional, and/or administration of nitrous oxide / oxygen mixture) will be given for the SP.

## **Extent of exposure**

A descriptive table for the number of lines by transducer, energy level, and treatment region will be produced for the SP, containing number of observed values (n obs), number of missing values (n miss), mean, standard deviation, median, quartiles, minimum, and maximum.

Frequency tables for premature treatment discontinuation and areas treated will be given for the SP.

## **Vital Signs**

A descriptive summary table will be presented for weight, height, and BMI by visit (i.e., Visits 1, 2, and 3 only; height will be collected at Visit 1 only).

## **Urine pregnancy test**

Results of urine pregnancy tests will be listed.

## **Device deficiencies**

All device deficiencies including device deficiencies for screening failures will be listed.

## **6.4 Special Statistical/Analytical Issues**

### **6.4.1 Discontinuations and Missing Data**

#### **Independent Photographic Review for Eyebrow Lift at Day 90 and Day 180**

For analysis of the primary and secondary effectiveness endpoints regarding Independent Photographic Review for Eyebrow lift, the following procedure for incomplete data from the independent evaluators will be applied:

[figure not shown]
- If data from all three independent evaluators is missing, the outcome of the subject will be set to missing.
- If the result of two out of three evaluators is missing, the outcome of the subject will be set to missing.

- If the result of one evaluator is missing and the other two evaluators agree on the assessment “Eyebrow Lift” then the outcome of the subject is set to “lift” for all analyses.
- If the result of one evaluator is missing and the other two evaluators agree on the assessment “No Eyebrow Lift” then the outcome of the subject is set to “no lift” for all analyses.
- If the result of one evaluator is missing and the other two evaluators disagree, then the outcome of the subject will be set to missing.

For treated subjects with missing outcome, the multiple imputation technique will be employed as described above for the primary and secondary analyses. For the worst case analysis, these subjects will be analyzed as having “no lift”.

All other effectiveness data will be analyzed as observed with no imputation of missing values. The denominator for percentages will be all subjects in the respective analysis set or population (i.e., missing data for binary or categorical variables will be presented as a separate possible category ‘Missing’).

CCI

### **Adverse events**

Missing data of the outcome will be imputed by “unknown”. For any other missing data of adverse events, a worst case strategy will be applied for all analysis tables. The intensity will be imputed

by the worst intensity “severe”, the causal relationship will be imputed by the worst relationship “related”.

#### **6.4.2 Interim Analyses**

In Stage 1, an initial cohort of 10 subjects was enrolled and treated with the 3.0 mm and 1.5 mm transducers. An interim database close and interim safety analysis through Day 14 was conducted for Stage 1 subjects. Safety analyses were performed on the SP. Effectiveness data were not included in the interim analysis.

Continuation to Stage 2 was paused during evaluation of the Day 14 safety data from Stage 1 subjects. At the conclusion of the safety assessment for Stage 1, expansion to use the 4.5 mm transducers was considered based on the totality of information available from the Stage 1 safety data, MDR analysis, and the mitigation measures/strategies proposed for this IDE based from the MDR analysis. All Stage 1 subjects participated until study end at 90 days ( $\pm$  7 days) or 180 days ( $\pm$  14 days) if reconsented for extended participation.

The interim analysis was only intended to obtain safety data for the first 10 subjects treated before starting recruitment for Stage 2. The interim analysis was not proposed to modify the study design, statistical analyses, or sample size, or for study termination, as this was not an adaptive study design. Since no effectiveness data were analyzed at interim, the interim analysis did not compromise the integrity of the study’s effectiveness data, and it did not bias the final effectiveness analysis.

A separate statistical analysis plan for the interim analysis was written.

#### **6.4.3 Multiple Comparisons/Multiplicity**

Primary analysis consists of two conditions which both need to be fulfilled to be able to claim effectiveness, therefore no adjustment of the type-1 error is needed.

#### **6.4.4 Examination of Subgroups**

The primary endpoint of observed cases will be additionally analysed by the different subgroups as described in section 6.1.1.3. Similar subgroups will be used for the secondary endpoint Independent Photographic Review for Eyebrow Lift at Day 180.

The safety endpoints for incidences of TEAEs using the SP will be descriptively summarized by Fitzpatrick skin type (I-III versus IV-VI) and race, as described in section 6.2.2.

Subjects with multiple origins (races) will be presented within a separate subgroup category “More than One Race”.

[figure not shown]
No statistical comparison of subgroups is planned.

#### **6.4.5 Pooling of Sites**

Analysis will be performed on pooled data across all investigational sites.

Treatment site will be used as explanatory variable for the multiple imputation model. In case it turns out that convergence of the model cannot be accomplished, the two smallest sites will be merged and a new model will be calculated. This process will be repeated until convergence is established. The pooled site will be coded as ‘0099999’.

CCI

CCI

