## 2 Clinical Trial Design and Objectives

### 2.1 Clinical Study Design

This is a 180-day, prospective, evaluator-blind, multicenter, staged, confirmatory study designed to evaluate the safety and effectiveness of the Octave System in lifting the brow and improving the appearance of the face and neck. Approximately 50 subjects will be enrolled at up to five investigational sites in the United States.

All Fitzpatrick skin types (FST) will be eligible for study enrollment. It is estimated that approximately 85% of the total sample size will consist of subjects with a FST I, II, or III, and approximately 15% of subjects will be FST IV, V, or VI. Subjects enrolled will be healthy male or female subjects, aged 35 to 65 years at the time of screening, with mild to moderate eyebrow/upper-face laxity and fine lines, wrinkles, and laxity of the mid- to lower face and neck that are amenable to improvement with non-invasive intervention and are not severe enough for surgical intervention.

In this non-comparative, staged, confirmatory study, investigators and subjects will not be blinded to treatment, subjects will not be randomized, and all enrolled subjects will receive a single Octave-Ultherapy treatment of the brow, upper, mid, and lower face, and neck. Subjects in Stage 1 (n = 10) will receive treatment with one transducer **CCI** at energy level 4 and one transducer **CCI** at energy level 2. Remaining subjects in Stage 2 will receive treatment with three transducers **CCI** at energy level 4 and one transducer **CCI** at energy level 2. In Stage 1, an initial cohort of subjects will be enrolled, safety data will be assessed to Day 14, and subjects will participate until study end at Day 90 or Day 180 if reconsented for extended participation. In Stage 2, all enrolled subjects will be followed for 180 days. In addition, to reduce potential bias associated with using only treated-subject photographs for evaluation, photographs of approximately 25 untreated individuals, who meet selected appearance criteria, will be collected at two different time points and subsequently paired for evaluation by the independent, blinded

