#### 6.1.1 Primary Effectiveness Endpoint

##### 6.1.1.1 Primary analysis

The primary endpoint of the study is the proportion of treated subjects with eyebrow lift by comparing photographs taken at Day 90 (post-treatment) with baseline (pre-treatment) photographs.

Each independent evaluator will assess “Eyebrow Lift”, “No Eyebrow Lift” or “Cannot Evaluate” between Photograph 1 (baseline) and Photograph 2 (post-baseline). Photograph 1 will be identified, and the independent evaluators will be blinded to the random distribution of treated versus untreated status of the comparator Photograph 2 (i.e., Day 90 post-treatment among treated subjects or post-baseline for untreated individuals). Lift will be declared if at least two blinded evaluators indicate “Eyebrow Lift” for the comparator photograph. In case at least two evaluators declare a photograph as not assessable (i.e., “Cannot Evaluate” is ticked), the corresponding lift score over all evaluators will be set to missing for the primary analysis. In case one evaluator rates a photograph as “Cannot Evaluate” and the other two evaluators disagree, the overall lift score will be set to “No Lift”.

The point estimate for the proportion of subjects fulfilling the primary endpoint will be described by frequency statistics for the ITT subset.

[figure not shown]
Effectiveness is established if:

[figure not shown]
- A. the point estimate is  $\geq 65\%$  and
- B. the lower bound of the one-sided 95% Wilson CI is  $> 50\%$ .

In addition, the proportion of untreated individuals fulfilling the primary endpoint will be calculated. It is expected that the point estimate for the proportion of untreated individuals is  $< 50\%$ .

Missing data, including a missing primary endpoint assessment in subjects with unacceptable (i.e. unassessable) or missing photographs at baseline or Day 90, will be imputed by multiple imputation. In case of complete data, no multiple imputation will be performed and the primary analysis is based on complete data for the ITT.

Imputation is done 50 times using a fully conditional specification logistic regression method, as implemented in SAS PROC MI with statement FCS LOGISTIC, and will use the investigational site and the baseline characteristics age and BMI as independent variables.

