In a first step a total of  $m=50$  imputed datasets will be generated, where missing data in the primary endpoint (lift over all evaluators) is modelled via logistic regression based on input variables site, age and BMI at baseline. 

  response is coded as ("no lift", "lift"). The lower bound of the one-sided 95% Wilson CI ([WL, WU]) will be calculated using the following steps, as detailed in [1]:

1. The mean sample response  $\hat{p}_{Imp}$  and sample variance  $\hat{U}_{Imp}$ ,

$$\hat{U}_{Imp} = \frac{\hat{p}_{Imp} (1 - \hat{p}_{Imp})}{n},$$

will be calculated for each of the  $m=50$  imputed datasets with sample size  $n$ .

2. The overall mean  $\bar{p}_m$  and variance  $\bar{U}_m$  over all imputed datasets will be calculated:

$$\bar{p}_m = \frac{1}{m} \sum_{Imp=1}^m \hat{p}_{Imp},$$

$$\bar{U}_m = \frac{1}{m} \sum_{Imp=1}^m \hat{U}_{Imp}.$$

These will be used to obtain  $B_m$ ,

$$B_m = \frac{1}{m-1} \sum_{Imp=1}^m (\hat{p}_{Imp} - \bar{p}_m)^2,$$

the between-sample variance.

3. The lower boundary of the one-sided 95% Wilson CI (WL and WU) will be calculated as

$$\left[ \frac{2\bar{p}_m + \frac{t^2}{n} + \frac{t^2 r_m}{n}}{2 \left( 1 + \frac{t^2}{n} + \frac{t^2 r_m}{n} \right)} - \sqrt{\frac{\left( 2\bar{p}_m + \frac{t^2}{n} + \frac{t^2 r_m}{n} \right)^2}{4 \left( 1 + \frac{t^2}{n} + \frac{t^2 r_m}{n} \right)^2} - \frac{\bar{p}_m^2}{1 + \frac{t^2}{n} + \frac{t^2 r_m}{n}}} \right],$$

where  $t$  denotes the 0.95 quantile of the t-distribution with degrees of freedom  $\nu$ ,

$$\nu = (m - 1) \left( 1 + \frac{1}{r_m} \right),$$

and with

$$r_m = \left( 1 + \frac{1}{m} \right) \frac{B_m}{U_m}.$$

The study is considered successful, and consequently effectiveness is established, if the parameter estimate  $\bar{p}_m \geq 65\%$  (condition A), and the lower limit of the one-sided 95% Wilson CI exceeds the margin of 50% (condition B).

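### The imputation model merges sites only on non-convergence, so a site with only lift results can pass that check and have its missing outcomes imputed as lift about half the time

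*SAP*

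**What the plan says.** SAP 6.1.1.1 fixes the imputation method: "Imputation is done 50 times using a fully conditional specification logistic regression method, as implemented in SAS PROC MI with statement FCS LOGISTIC". The missing overall lift result "is modelled via logistic regression based on input variables site, age and BMI at baseline". Imputation runs only when something is missing: "In case of complete data, no multiple imputation will be performed". The pooled estimate must reach 65%, and its one-sided 95% Wilson lower bound must exceed 50%.

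The number of sites is open: "Approximately 50 subjects will be enrolled at up to five investigational sites in the United States" (SAP 2.1). SAP 3 plans for 40 evaluable subjects and at most 10 lost.

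SAP 6.4.5 governs small sites: "In case it turns out that convergence of the model cannot be accomplished, the two smallest sites will be merged", and "This process will be repeated until convergence is established". It does not say whether a site with only one observed outcome counts as non-convergence. It sets no minimum site size and names no penalised or augmented likelihood. The code that follows the model description in 6.1.1.1 is absent from the public text. SAP 6.1.2 reuses the method for Day 180.

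**The concern.** Five sites sharing 40 observed outcomes have about 8 each. At 72% lift, some site may well show lift in all 8. Maximum likelihood then has no finite estimate for that site's effect: the coefficient drifts upward and its standard error grows much faster. Because the likelihood flattens, a gradient-based stopping rule can report a normal finish. FCS imputation draws the coefficients from their estimated distribution. With a huge standard error the draw is about as often strongly negative as strongly positive, so the site's missing subjects are imputed as lift about half the time, although everyone observed there had lift.

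The merging rule would repair this, but it waits for a non-convergence that may never be reported. The resulting estimate is then compared with two fixed limits, so the same photograph ratings could pass or fail according to a software setting that the plan does not state.

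**Working it through.** **1. The plan's own figure.** At n = 40 the smallest passing count is 26 (65.0%, Wilson lower bound 52.0%; 25 gives 49.5%). Exact binomial power at 72% is 87.6%, which agrees with the SAP's claim of at least 85%. Type I error at 50% is 4.0%. The SAP gives no figure for imputation.

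**2. How often a site is all lift.** With 8 observed per site, 0.72^8 = 0.072, and 1 − (1 − 0.072)^5 = 31%. With 10 observed per site it is 17%. With three sites of about 13, 0.72^13 = 0.014, and 1 − (1 − 0.014)^3 = 4%.

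**3. What is imputed there.** Take 8 of 8 lift at one of five sites and an ordinary maximum likelihood fit. A relative-gradient criterion of 1e-8 is met after about 17 iterations, with linear predictor about 18 and standard error about 3,100. The chance that a draw is positive is Φ(18/3,100) = Φ(0.006), or about 50%. Imputed lift is 51% at 1e-8, 52% at 1e-6, 61% at 1e-4 and 76% at 1e-3. Under a parameter-change criterion the step stays at 1.0 per iteration, the fit never converges, and SAP 6.4.5 would act.

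**4. Effect on the pooled estimate.** Simulation of the SAP's procedure (50 imputations, the SAP's Wilson formula, 50 subjects, 72% lift, 1e-8 criterion, 2,000 to 3,000 trials per scenario). Site sizes, missingness at random, and lift unrelated to site, age or BMI are assumptions. Here *affected* means that an all-lift site has a missing outcome. The last two columns compare the model as written with the SAP's repeated merging triggered by a one-outcome site.

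| Sites | Missing | Trials affected | Estimate minus observed proportion, affected trials | Estimate, as written → merged | Success in affected trials, as written → merged |
|---|---|---|---|---|---|
| 5 × 10 | 10 | 32% | −3.1 points | 73.5% → 75.9% | 92.3% → 95.4% |
| 5 × 10 | 5 | 20% | −1.5 | 75.5% → 77.0% | 96.2% → 97.0% |
| 18/14/10/5/3 | 10 | 52% | −2.0 | 71.8% → 73.3% | 84.8% → 87.6% |
| 18/14/10/5/3 | 5 | 31% | −1.1 | 73.2% → 74.1% | 90.8% → 91.8% |

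Imputed lift at the all-lift site was 50 to 51% as written and 74 to 81% after merging. With two sites of 25 the problem arises in about 0.2% of trials. Monte Carlo error is about 1 point on rates.

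**5. Over all trials.** The estimate lies about 0.6 to 1.6 points below the observed proportion. Part of this is not separation: trials without an affected site also show about 0.4 to 0.8 points. Merging the one-outcome site raises the overall mean by about 0.3 to 0.8 points and overall success by 0 to 2 points.

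**6. Direction.** At a true rate of 50% with 10 missing, success is declared in 2.2% of trials as written and 2.5% with merging (equal sites), and in 1.8% and 2.2% (unequal sites). False-positive risk is not raised.

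**7. Near the limit.** Suppose 27 of 40 observed have lift (67.5%), with 2 missing at each of five sites and one site 8 of 8. The other sites have 19/32 = 59.4%. Imputing half lift at the full site gives 27 + 2 × 0.5 + 8 × 0.594 = 32.75, or 65.5%. Imputing lift there gives 33.75, or 67.5%. In repeated imputations of this case success was declared about 70% of the time as written, and 99% or more with site left out.

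**The case against.** The strongest reply is that every step is conditional. With the code unseen, ordinary maximum likelihood is an inference, and an augmented-likelihood option may already be there. The 50% figure needs a tight gradient criterion. This stands, so a reader should not infer that any all-lift site will be imputed at half lift.

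A reader might also infer that the SAP's merging would leave the affected site alone because it joins the two smallest sites. The first merge can miss it, but SAP 6.4.5 repeats until the model converges. If separation counted as non-convergence, the existing rule would largely remove the problem. The gap is the trigger.

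Nor is the 3-point figure a bias against the true rate. Trials with an all-lift site tend to have high observed lift, and their mean estimate as written (71.8 to 75.5%) is close to or above the assumed 72%.

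Finally, the observed-case and worst-case analyses in SAP 6.1.1.2 do not use this model, and the by-site tables in 6.1.1.3 would reveal an all-lift site. That makes the problem visible afterwards, but the primary decision would still rest on the imputed estimate.

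**Conclusion.** The concern holds in conditional form. SAP 6.4.5 ties merging to non-convergence without saying whether a one-outcome site qualifies. With five small sites, 5 to 10 missing outcomes and 72% lift, about 20 to 50% of trials would meet the condition; with two or three sites it is rare. If the fit is ordinary maximum likelihood and is accepted as converged, the primary estimate drops by about 1 to 3 points against the observed proportion in those trials (1.5 to 3 with equal sites), or by 0.9 to 2.4 points against merging.

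The consequence is lost power, roughly 1 to 3 points of success probability in affected trials. The documents and calculations do not support reading it as a threat of false success or as a certain bias. It is worth correcting because a result near 65% could turn on an unstated stopping rule, and the correction costs almost nothing.

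**What to change.** In SAP 6.4.5, state that before imputing, any site whose observed subjects all have the same lift result counts as non-convergence and is itself merged with the smallest other site, repeated until no such site remains. Alternatively, state that an augmented likelihood is used; if the unseen code already does this, one line in the text settles the point. Apply the same rule to the Day 180 analysis in SAP 6.1.2.

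Dropping site from the model is optional. It performed well here, but the simulations assumed that lift does not differ by site, and the documents do not establish that.

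The cost is one or two sentences and no new data, ideally before the photograph ratings are analysed. The downside is slightly less site-specific imputation when a merge occurs.
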